### 6.1 Serious Adverse Events

A *Serious Adverse Event (SAE)* is any untoward medical occurrence that at any dose:

- results in death
- is life-threatening (defined as an event in which the subject was at risk of death at the time of the event; it does not refer to an event which hypothetically might have caused death if it were more severe)
- requires inpatient hospitalization or causes prolongation of existing hospitalization (see **NOTE** below)
- results in persistent or significant disability/incapacity
- is a congenital anomaly/birth defect
- is an important medical event (defined as a medical event(s) that may not be immediately life-threatening or result in death or hospitalization but, based upon appropriate medical and scientific judgment, may jeopardize the subject or may require intervention [eg, medical, surgical] to prevent one of the other serious outcomes listed in the definition above.) Examples of such events include, but are not limited to, intensive treatment in an emergency room or at home for allergic bronchospasm; blood dyscrasias or convulsions that do not result in

hospitalization.) Potential drug induced liver injury (DILI) is also considered an important medical event. (See [Section 6.6](#) for the definition of potential DILI.)

Suspected transmission of an infectious agent (eg, pathogenic or nonpathogenic) via the study drug is an SAE.

Although pregnancy, overdose, cancer, and potential drug induced liver injury (DILI) are not always serious by regulatory definition, these events must be handled as SAEs. (See [Section 6.1.1](#) for reporting pregnancies).

Any component of a study endpoint that is considered related to study therapy (eg, death is an endpoint, if death occurred due to anaphylaxis, anaphylaxis must be reported) should be reported as SAE (see [Section 6.1.1](#) for reporting details).

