### **3.5 Discontinuation of Subjects following any Treatment with Study Drug**

Subjects MUST discontinue investigational product (and non-investigational product at the discretion of the investigator) for any of the following reasons:

- Subject's request to stop study treatment
- Recurrence (local, regional or distant)
- Any clinical adverse event (AE), laboratory abnormality or intercurrent illness which, in the opinion of the investigator, indicates that continued participation in the study is not in the best interest of the subject
- Termination of the study by Bristol Myers Squibb (BMS)
- Loss of ability to freely provide consent through imprisonment or involuntarily incarceration for treatment of either a psychiatric or physical (eg, infectious disease) illness
- Unblinding a subject for any reason (emergency or non-emergency)
- Additional protocol specified reasons for discontinuation (see [Section 4.5.7](#)).

In the case of pregnancy, the investigator must immediately notify the BMS Medical Monitor/designee of this event. In most cases, the study drug will be permanently discontinued in an appropriate manner. If the investigator determines a possible favorable benefit/risk ratio that warrants continuation of study drug, a discussion between the investigator and the BMS Medical Monitor/designee must occur.

All subjects who discontinue study drug should comply with protocol specified follow-up procedures as outlined in [Section 5](#). The only exception to this requirement is when a subject withdraws consent for all study procedures including post-treatment study follow-up or loses the ability to consent freely (ie, is imprisoned or involuntarily incarcerated for the treatment of either a psychiatric or physical illness).

If study drug is discontinued prior to the subject's completion of the study, the reason for the discontinuation must be documented in the subject's medical records and entered on the appropriate case report form (CRF) page.

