### **6.1.1 Serious Adverse Event Collection and Reporting**

Sections 5.6.1 and 5.6.2 in the Investigator Brochure (IB) represent the Reference Safety Information to determine expectedness of serious adverse events for expedited reporting. Following the subject's or the legal representative's written consent to participate in the study, all SAEs, whether related or not related to study drug, must be collected, including those thought to be associated with protocol-specified procedures. All SAEs must be collected that occur during the screening period and within 100 days of discontinuation of dosing. Subjects who are randomized and never treated with study drug, must have SAEs collected for 30 days from the date of randomization. If applicable, SAEs must be collected that relate to any later protocol-specified procedure (eg. a follow-up skin biopsy).

The investigator should report any SAE that occurs after these time periods and that is believed to be related to study drug or protocol-specified procedure.

An SAE report should be completed for any event where doubt exists regarding its seriousness.

If the investigator believes that an SAE is not related to study drug, but is potentially related to the conditions of the study (such as withdrawal of previous therapy or a complication of a study procedure), the relationship should be specified in the narrative section of the SAE Report Form.

SAEs, whether related or not related to study drug, and pregnancies must be reported to BMS (or designee) within 24 hours of awareness of the event, SAEs must be recorded on the SAE Report Form; pregnancies on a Pregnancy Surveillance Form (electronic or paper forms). The preferred method for SAE data reporting collection is through the eCRF. The paper SAE/pregnancy surveillance forms are only intended as a back-up option when the eCRF system is not functioning. In this case, the paper forms are to be transmitted via email or confirmed facsimile (fax) transmission to:

**SAE Email Address:** Refer to Contact Information list.

**SAE Facsimile Number:** Refer to Contact Information list.

For studies capturing SAEs through electronic data capture (EDC), electronic submission is the required method for reporting. The paper forms should be used and submitted immediately, only in the event the electronic system is unavailable for transmission. When paper forms are used, the original paper forms are to remain on site.

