## 6.6 Safety Analyses - Closed Report Only

Safety analyses will be performed in all treated subjects. Descriptive statistics of safety will be presented using NCI CTCAE version 4.0 by treatment group. All on-study AEs, drug-related AEs, SAEs, and drug-related SAEs, AEs leading to discontinuation, drug-related AEs leading to discontinuation, select AEs and drug-related select AEs will be tabulated using worst grade per NCI CTCAE v 4.0 criteria by system organ class and preferred term. On-study lab parameters including hematology, chemistry, liver function, and renal function as well as electrolytes will be summarized using worst grade NCI CTCAE v 4.0 criteria.

Unless otherwise noted, the analyses of AEs will include events occurring on-study (i.e., from first day of study treatment and no later than 30 days following the last day of study treatment, or events entered on an AE form but with a missing onset date).

AEs with a relationship to study therapy of related or unknown (not reported) will be considered drug-related.

The frequency of on-study AEs, coded using MedDRA system organ classes and preferred terms will be calculated.

Laboratory parameters will include hemoglobin, platelets, neutrophils, WBC, lymphocytes, AST, ALP, ALT, total bilirubin, creatinine, amylase and lipase as well as electrolytes (sodium, calcium, magnesium and potassium).

The following summaries will be produced:

- Summary of Any Adverse Events by Worst CTC Grade
- Summary of Drug-Related Adverse Events by Worst CTC Grade
- Summary of Serious Adverse Events by Worst CTC Grade
- Summary of Drug-Related Serious Adverse Events by Worst CTC Grade
- Summary of Adverse Events Leading to Discontinuation by Worst CTC Grade
- Summary of Drug-Related Adverse Events Leading to Discontinuation by Worst CTC Grade
- Summary of Any Select Adverse Events by Worst CTC Grade and by Category
- Summary of Drug-Related Select Adverse Events by Worst CTC Grade and by Category
- Intensity Rate of Serious Adverse Events by Onset Period
- Summary of incidence of deaths and reason for death.
- On-study Laboratory Parameters Summary by Worst CTC grade: Changes from Baseline Grade - SI Units

Death, reason for death and adverse events leading for discontinuation will be also listed.

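### Nothing in the plan says whether a melanoma recurrence judged unrelated to study drug is an SAE, so the all-causality SAE tables can contain primary-endpoint events to an unknown extent

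*Protocol*

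**What the plan says.** **Reporting rules.** Protocol 6.1 lists cancer among events that are always treated as serious: "Although pregnancy, overdose, cancer, and potential drug induced liver injury (DILI) are not always serious by regulatory definition, these events must be handled as SAEs". A following paragraph covers endpoint events: "Any component of a study endpoint that is considered related to study therapy" should be reported as an SAE, with a death from anaphylaxis as the example. Section 6.1.1 applies no causality filter: "all SAEs, whether related or not related to study drug, must be collected". It sets the period ("All SAEs must be collected that occur during the screening period and within 100 days of discontinuation of dosing") and a tie-break ("An SAE report should be completed for any event where doubt exists regarding its seriousness"). The hospitalization exceptions in 6.1 include admission to give anticancer therapy but do not mention admission for recurrence.

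**Endpoint.** Protocol 8.3.1 counts recurrence, new primary melanoma and death as RFS events. Section 5.4.1 defines recurrence as new melanoma lesions. Section 3.5 requires study drug to stop for "Recurrence (local, regional or distant").

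**Tabulation.** Protocol 8.4.3 tabulates all SAEs and treatment-related SAEs by arm. Section 6.6 of the DMC SAP plans "Summary of Serious Adverse Events by Worst CTC Grade" and a drug-related counterpart, for events from first dose and "no later than 30 days following the last day of study treatment". Neither document excludes recurrence or neoplasm terms.

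**The concern.** Safety is a secondary objective, and Protocol 8.3.2 measures it partly by SAE incidence. The DMC weighs benefit against risk with the closed-report tables in front of it. The trial's hypothesis is that the arms differ in recurrence. If some recurrences are filed as SAEs, the all-causality SAE rate mixes toxicity with the primary endpoint. The amount of mixing then depends on how each site reads 6.1, not on a rule in the plan. A reader of the per-arm total of subjects with any SAE could not tell which part of a difference is toxicity.

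**Working it through.** **1. Can a recurrence enter the table under the rules as written?** Elsewhere the protocol adds the limit when it means it: non-melanoma malignancies in the exclusion criteria, second non-melanoma primary cancer in Table 8.3.1-1, non-melanoma cancers in the follow-up text. The cancer sentence in 6.1 carries no such limit, so it can be read to cover new melanoma lesions. The endpoint sentence tells sites to report related components and says nothing of unrelated ones. Section 6.1.1 removes causality as a filter and tells sites to report when seriousness is in doubt. Even on a narrow reading of cancer, a recurrence that needs inpatient admission meets the ordinary hospitalization criterion. So the answer is yes, it can. Because drug stops at recurrence, one found on treatment lies close to the last dose and can fall inside the 30-day window.

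**2. Design inputs.** The documents state no SAE rate and no share of recurrences reported as SAEs, so there is no stated figure to reproduce on this point. The design figures borrowed below do reproduce. For 450 events and hazard ratio 0.75, power is Φ(|ln 0.75|·√450/2 − 1.960) = Φ(1.091) = 86.2%, or 85.6% with the interim look (stated: at least 85%). Lan-DeMets O'Brien-Fleming at 350/450 gives 0.0221 and critical hazard ratio 0.783 at interim, then 0.0435 and 0.827 at the final analysis (stated: 0.022, 0.78, 0.043, 0.83).

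**3. RFS events within the longest window.** Assume exponential RFS, 450 per arm and hazard ratio 0.75. Follow-up at the interim is uniform from 18 to 25.5 months (18 plus 7.5 months of accrual). Solve for the ipilimumab hazard λ so that the average of ½(1−e^(−λT)) + ½(1−e^(−0.75λT)) equals 350/900. This gives λ = 0.02607 per month. By 13 months (one year of treatment plus about one month):
- ipilimumab: 1 − e^(−0.02607×13) = 28.7%, about 129 of 450
- nivolumab: 1 − e^(−0.75×0.02607×13) = 22.4%, about 101 of 450
- difference: 6.3 points

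**4. Effect on the any-SAE rate.** Let b be the true SAE rate, equal in both arms and independent of recurrence, and s the share of these events filed as SAEs. The false gap is s(1−b)×6.3.

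| s | b = 10% | b = 40% |
|---|---|---|
| 100% | 5.7 | 3.8 |
| 50% | 2.8 | 1.9 |
| 25% | 1.4 | 0.9 |
| 10% | 0.6 | 0.4 |
| 0% | 0 | 0 |

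**5. Direction.** Suppose a share d of the ipilimumab arm stops at 3 months, so its window closes at about 4 months, and nobody stops early on nivolumab. By 4 months, 1 − e^(−0.02607×4) = 9.9% have an event. The ipilimumab in-window rate is (1−d)×28.7 + d×9.9, and the 6.3-point difference becomes:
- d = 20%: +2.5
- d = 40%: −1.2
- d = 50%: −3.1

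It crosses zero at d = 6.3/(28.7 − 9.9), about one third.

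**6. Shape.** The plan assumes a delayed effect and a cure fraction but does not give their values. Refitting λ to 350/900 with a delay of 3 or 6 months before the hazard ratio applies gives 4.7 or 3.2 points in place of 6.3. With a cure fraction of 30% or 50% in the ipilimumab arm and a constant hazard ratio between whole arms (S_niv = S_ipi^0.75), it is 6.6 or 7.4. So 6.3 is an illustration and not a bound.

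**The case against.** **The two rules do not contradict each other.** A reader might infer that unrelated endpoint events are exempt and that this clashes with the cancer sentence. The text does not say so: it tells sites to report related components and stops there. Its example concerns the cause of a death, not recurrence. What remains is an ambiguity.

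**Cancer may mean a new cancer.** It stands beside pregnancy, overdose and liver injury, all of them new occurrences, whereas every subject enters with resected melanoma. Recurrence has its own case report forms, and completion guidelines that we cannot see may settle the matter. This is a fair reading, and it rules out saying that sites must report, or did report, every recurrence. It does not remove the gap in the protocol.

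**The tables expose the events anyway.** SAEs are shown by system organ class and preferred term, so reported recurrences appear in their own rows. The drug-related tables and the select-AE list, which has no melanoma terms, are also available. That is true, but rows reveal the events without taking them out of the per-arm total of subjects with any SAE.

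**Safety is descriptive and the SAP covers DMC reports only.** Both are correct. No test of SAE rates is planned, and the SAP for the clinical study report, which Protocol section 8 mentions, may already handle this.

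**It is late.** All subjects were off treatment by December 2016, the planned analyses used the January 2020 lock, and the last DMC meeting was in April 2020. A wording change can do little for on-treatment reporting. A repeat table from coded terms is still possible.

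**Conclusion.** The point holds as a gap. The rules as written allow unrelated recurrences and new primary melanomas into the all-causality SAE tables, and nothing in the two documents takes them out. The false gap runs from near 0 to about 4-6 points. The upper end needs every in-window RFS event to be filed as an SAE, exponential RFS with hazard ratio 0.75, equal true SAE rates of 10-40%, and no early stopping. The model also counts deaths as recurrences and uses randomized rather than treated subjects.

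Two stronger readings are not supported. A reader might infer that the arm with more recurrences will look more toxic, but the window is tied to the last dose, so earlier stopping in that arm shrinks the effect and can reverse it. A reader might also infer that the summary of AEs leading to discontinuation is contaminated, but Protocol 3.5 lists recurrence as a reason separate from adverse events, so this is not shown. Drug-related SAE tables are largely protected. RFS, OS, alpha and power are not affected. This is a cheap improvement to the safety reporting and not a flaw in the primary analysis.

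**What to change.** **SAP 6.6 and Protocol 8.4.3.** Add a second all-causality SAE summary by arm, shown next to the full table. It excludes a prespecified list of preferred terms for melanoma recurrence, metastasis, progression and new primary melanoma where the event is not considered drug-related. Repeat the summary of AEs leading to discontinuation in the same way only if such terms appear in it. Apply the same rule in the SAP for the clinical study report if it has none.

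**Protocol 6.1.** Reconcile the cancer sentence with the endpoint-component sentence: state whether a recurrence or new primary melanoma judged unrelated is to be reported as an SAE. With all subjects off treatment, this mainly documents how the existing data should be read.

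**Cost.** One extra table, one or two sentences and a term list. The list must be fixed before anyone reviews unblinded data. Because the full table stays, no safety information is lost.

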**NOTE:**

The following hospitalizations are not considered SAEs in BMS clinical studies:

- a visit to the emergency room or other hospital department < 24 hours, that does not result in admission (unless considered an important medical or life-threatening event)
- elective surgery, planned prior to signing consent
- admissions as per protocol for a planned medical/surgical procedure
- routine health assessment requiring admission for baseline/trending of health status (eg, routine colonoscopy)
- medical/surgical admission other than to remedy ill health and planned prior to entry into the study. Appropriate documentation is required in these cases
- admission encountered for another life circumstance that carries no bearing on health status and requires no medical/surgical intervention (eg, lack of housing, economic inadequacy, caregiver respite, family circumstances, administrative reason).
- Admission for administration of anticancer therapy in the absence of any other SAEs (applies to oncology protocols)

### **6.1.1 Serious Adverse Event Collection and Reporting**

Sections 5.6.1 and 5.6.2 in the Investigator Brochure (IB) represent the Reference Safety Information to determine expectedness of serious adverse events for expedited reporting. Following the subject's or the legal representative's written consent to participate in the study, all SAEs, whether related or not related to study drug, must be collected, including those thought to be associated with protocol-specified procedures. All SAEs must be collected that occur during the screening period and within 100 days of discontinuation of dosing. Subjects who are randomized and never treated with study drug, must have SAEs collected for 30 days from the date of randomization. If applicable, SAEs must be collected that relate to any later protocol-specified procedure (eg. a follow-up skin biopsy).

The investigator should report any SAE that occurs after these time periods and that is believed to be related to study drug or protocol-specified procedure.

An SAE report should be completed for any event where doubt exists regarding its seriousness.

If the investigator believes that an SAE is not related to study drug, but is potentially related to the conditions of the study (such as withdrawal of previous therapy or a complication of a study procedure), the relationship should be specified in the narrative section of the SAE Report Form.

SAEs, whether related or not related to study drug, and pregnancies must be reported to BMS (or designee) within 24 hours of awareness of the event, SAEs must be recorded on the SAE Report Form; pregnancies on a Pregnancy Surveillance Form (electronic or paper forms). The preferred method for SAE data reporting collection is through the eCRF. The paper SAE/pregnancy surveillance forms are only intended as a back-up option when the eCRF system is not functioning. In this case, the paper forms are to be transmitted via email or confirmed facsimile (fax) transmission to:

**SAE Email Address:** Refer to Contact Information list.

**SAE Facsimile Number:** Refer to Contact Information list.

For studies capturing SAEs through electronic data capture (EDC), electronic submission is the required method for reporting. The paper forms should be used and submitted immediately, only in the event the electronic system is unavailable for transmission. When paper forms are used, the original paper forms are to remain on site.

**SAE Telephone Contact** (required for SAE and pregnancy reporting): Refer to Contact Information list.

If only limited information is initially available, follow-up reports are required. (Note: Follow-up SAE reports should include the same investigator term(s) initially reported.)

If an ongoing SAE changes in its intensity or relationship to study drug or if new information becomes available, a follow-up SAE report should be sent within 24 hours to the BMS (or designee) using the same procedure used for transmitting the initial SAE report.

All SAEs should be followed to resolution or stabilization.

## **6.2 Nonserious Adverse Events**

A *nonserious adverse event* is an AE not classified as serious.

### **6.2.1 Nonserious Adverse Event Collection and Reporting**

The collection of nonserious AE (not only those deemed to be treatment-related) information should begin at initiation of study drug **and continue until 100 days from the last dose of study drug**. Non-serious AE information should also be collected from the start of a placebo lead-in period or other observational period intended to establish a baseline status for the subjects.

Nonserious AEs should be followed to resolution or stabilization, or reported as SAEs if they become serious (see [Section 6.1.1](#)). Follow-up is also required for nonserious AEs that cause withholding or discontinuation of study drug and for those present at the end of study treatment as

appropriate. All identified nonserious AEs must be recorded and described on the nonserious AE page of the CRF (paper or electronic).

Completion of supplemental CRFs may be requested for AEs and/or laboratory abnormalities that are reported/identified during the course of the study. Every adverse event must be assessed by the investigator with regards to whether it is considered immune mediated. For events which are potentially immune mediated, additional information will be collected on the subject's case report form.

### **6.3 Laboratory Test Result Abnormalities**

The following laboratory test result abnormalities should be captured on the nonserious AE CRF page or SAE Report Form (paper or electronic) as appropriate:

- Any laboratory test result that is clinically significant or meets the definition of an SAE
- Any laboratory test result abnormality that required the subject to have study drug omitted or discontinued
- Any laboratory test result abnormality that required the subject to receive specific corrective therapy.

It is expected that wherever possible, the clinical rather than laboratory term would be used by the reporting investigator (eg, anemia versus low hemoglobin value).

